A robust literature documents the efficacy of cognitive behavioral therapy for insomnia (CBT-I) compared to control conditions.⁷ Additionally, mounting evidence has shown that CBT-I is associated with improved depression outcomes, including higher rates of depression remission among participants with insomnia and depression,⁸ and lower depression symptom severity among non-pregnant adults with both insomnia and subclinical depression symptoms compared to digital attention-matched placebo control.⁹ In a single group study, participants reported significant improvements in subjective and objective sleep parameters and depression symptom severity after five weekly sessions.¹⁰ These results are promising, but the trial lacked a control group and therefore does not support causal inference.

Qualitative research shows that women report a preference for mental health care that includes flexible options. ¹¹ Thus, digital programs may be of particular interest during the perinatal period. A recent meta-analysis supports the efficacy of digital CBT-I for sleep compared to control. ¹² Sleepio is a digital CBT-I program associated with significantly greater improvements in sleep efficiency (among other sleep parameters) and depression symptom severity compared to both active control and treatment as usual conditions immediately post-intervention and at an 8-week follow-up. ^{13,14} The overarching goal of this project is to use a randomized control design to examine the efficacy of digital CBT-I (Sleepio) for sleep and mental health outcomes compared to treatment as usual among pregnant women with insomnia symptoms.

Objectives

- **Aim 1**: To test the hypothesis that participants randomized to digital CBT-I will demonstrate significantly greater improvements in subjective sleep outcomes, including insomnia symptom severity (primary outcome), sleep duration, sleep efficiency, global sleep quality, and insomnia caseness, compared to TAU participants.
- **Aim 2**: To test the hypothesis that participants randomized to digital CBT-I will experience significantly greater improvements in mental health outcomes, including depressive symptoms (primary) and anxiety symptoms, compared to TAU participants.

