Outcomes. The primary outcome is change in insomnia symptom severity (Insomnia Severity Index) from baseline to 10-weeks post-randomization. Secondary sleep outcomes include sleep efficiency (sleep diary), sleep duration (sleep diary), global sleep quality (Pittsburgh Sleep Quality Index), and insomnia caseness (Sleep Condition Indicator). Secondary mental health outcomes include depressive symptom severity (Edinburgh Postnatal Depression Scale) and anxiety (Generalized Anxiety Disorder Scale). We will additionally examine change to 18-weeks post-randomization, 36 weeks gestation, 3 months postpartum, and 6 months postpartum. Other, exploratory outcomes include birth outcomes, such as gestational age at delivery, APGAR scores, birthweight, and delivery method.

Participant timeline (See Figure). *Eligibility survey.* Individuals interested in participating will complete an electronic consent form describing the screening procedures. Next, participants will complete questionnaires to assess eligibility. Participants will complete a demographic measure, provide contact information, and indicate whether they agreed to be contacted for other research studies. Individuals who pass the eligibility survey will complete the study consent form and be given instructions to complete the sleep diaries.

Sleep diaries. Participants will receive email requests to complete sleep diaries on REDCap for seven consecutive days. Participants will indicate when they got in bed, how long it took to fall asleep, number of awakenings, duration of awakenings, final awakening time, and when they got out of bed. Participants who complete at least four diaries will be eligible to proceed to the orientation session.

Orientation. The primary goal of the phone orientation session, modeled after Goldberg and Kiernan (2005),¹⁵ is to promote participant retention by discussing the importance of the trial, required commitments, what to expect if randomized to digital CBT-I or TAU, the rationale of the control condition and random assignment, and the impact of attrition bias. Participants will describe personal pros and cons for participating in the trial, and will be given as much time as needed to decide whether to participate.

Baseline measures. Participants will complete baseline measures on the Qualtrics online survey system.

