Electronic health record recruitment. MyChart (APeX) will conduct a search for patients based on the study's inclusion and exclusion criteria. This is a completely computer-aided search, meaning the computer— not a person— searches patient charts. When a patient is identified as potentially eligible, they will receive an email from MyChart that asks them to log in to MyChart to read about a study in which they might be interested. The email is short and is the same for every recipient—it contains no patient-specific or study-specific information. When the patient logs into MyChart, there will be a "Research" tab with template information about research participation and how to opt out of receiving recruitment messages. The patient can click through to learn about the specific study to which they have been matched. The patient has the option of clicking a button to let the study team know that they are interested in learning more about the study. The study team will only receive information about the patient if the patient takes this action. If the patient clicks "No thanks" or simply does not respond, they will not be contacted by the study team or receive any follow-up emails from MyChart about the study, nor will their information be shared with the study team.

Assignment of interventions

Allocation. The blocked randomization sequence will be generated by an independent investigator using Sealed Envelope.²⁰ The randomization sequence and block sizes will be concealed from study staff. The randomization sequence will be kept on an electronic file inaccessible to the study staff. Once a participant completes baseline measures, study staff will request the allocation assignment from the independent investigator. Study investigators and staff will not be able to influence randomization or have access to future allocations.

Blinding. For study administration purposes, staff will be unblinded to participant condition assignment after allocation. Study staff will be blinded to outcomes during the trial. Participants will be unblinded to condition assignment due to the nature of the comparison group, which is not an active comparator. The study statistician will remain blinded to condition assignment for all primary analyses.

Data collection, management, and analysis

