Statistical methods. Independent samples t-tests and chi-square tests will be used to examine between-group differences in baseline sociodemographic and clinical characteristics. Linear mixed effects models will be used to examine whether within-woman changes in sleep and mental health outcomes differ between the digital CBT-I and treatment as usual groups. 30 Models will include the sleep and mental health outcomes as the dependent variables, along with time, intervention group, and time by group interactions as the predictors. The models also will include random intercepts to accommodate the correlation among the repeated responses within women. The regression coefficients of time by intervention group interactions measure the differences in the rate of within-woman change in the outcomes between the two intervention groups. We will assess the statistical significance of the time by intervention group interaction using likelihood ratio tests. The primary analysis will assess differences in changes in insomnia symptom severity from baseline to post-intervention with time measured in weeks. Secondary analyses of additional sleep and mental health outcomes will use the same time scale. Additionally, we will examine change from baseline to follow-up.

Monitoring

Harms. Adverse events that are spontaneously reported by participants will be characterized by an independent safety officer as unexpected or expected, and causes will be characterized as definitely related, probably related, possibly related, or unrelated to study participation. Adverse events that are determined to be unrelated to study participation are documented but not reported to the IRB. All other adverse events are reported to the IRB.

Ethics and Dissemination

Research ethics approval

The research protocol will be submitted to the UCSF institutional review board for approval.

Protocol amendments

Protocol modifications will be communicated to all study investigators and approved by the IRB prior to implementation, and the trial registry will be updated accordingly.

Consent or assent

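### Statistician blinding is promised only for the primary analyses, leaving 26 (or 25) of 27 Aim 1 and 2 comparisons without it; extend it and lock all scripts first

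*Combined protocol and SAP*

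**What the plan says.** Under Assignment of interventions, the Blinding paragraph makes one commitment about the analyst: "The study statistician will remain blinded to condition assignment for all primary analyses". The same paragraph says: "For study administration purposes, staff will be unblinded to participant condition assignment after allocation". It adds that participants know their arm, and that staff do not see outcomes while the trial is running.

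Three sections bear on what counts as primary:

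- Outcomes: "The primary outcome is change in insomnia symptom severity (Insomnia Severity Index) from baseline to 10-weeks post-randomization".
- Statistical methods: "The primary analysis will assess differences in changes in insomnia symptom severity from baseline to post-intervention with time measured in weeks".
- Objectives: Aim 1 covers "insomnia symptom severity (primary outcome), sleep duration, sleep efficiency, global sleep quality, and insomnia caseness, compared to TAU participants", and Aim 2 covers "mental health outcomes, including depressive symptoms (primary) and anxiety symptoms, compared to TAU participants". Outcomes, by contrast, says "Secondary mental health outcomes include depressive symptom severity (Edinburgh Postnatal Depression Scale) and anxiety (Generalized Anxiety Disorder Scale").

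For everything else, Statistical methods says: "Secondary analyses of additional sleep and mental health outcomes will use the same time scale". One further sentence says that change to follow-up will also be examined.

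**The concern.** Every Aim 1 and 2 outcome is self-reported by women who know their arm, and staff know the arm too. At the analysis stage, the statistician's blinding is the only safeguard the plan states, and its stated scope stops at the primary analyses.

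The secondary and follow-up comparisons carry the mental health claims and any claim that benefit lasts. They are also where the plan leaves the most to be decided. If those decisions are made by someone who knows the arms and has seen the primary result, a reader cannot rule out that the choices were steered, even unintentionally.

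**Working it through.** The plan gives no figure to reproduce on this point. The check is a count, followed by a comparison of what is fixed with what is open.

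**1. Outcomes.** From Objectives: Aim 1 has 5 (ISI, sleep duration, sleep efficiency, PSQI, caseness on the SCI) and Aim 2 has 2 (EPDS, GAD-7). Total 5 + 2 = 7.

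**2. Visits.** From Outcomes: week 10, week 18, gestational week 36, and three and six months after birth, so 5. Follow-up assessments names the diaries only at week 10, so the two diary outcomes have one visit each.

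**3. Comparisons.** (5 questionnaire outcomes × 5 visits) + (2 diary outcomes × 1 visit) = 25 + 2 = 27.

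**4. Comparisons without stated analyst blinding.**

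- ISI at week 10 is the only primary (Outcomes, Statistical methods): 27 − 1 = 26, or 96%. At week 10 alone, 6 of 7.
- EPDS at week 10 is also primary (Objectives): 27 − 2 = 25, or 93%. At week 10 alone, 5 of 7.
- Most generous reading, with ISI and EPDS primary at all five visits: 27 − 10 = 17, or 63%. Outcomes and Statistical methods tie the primary to week 10 or post-intervention, so they do not support this reading. It shows only that the gap survives it.

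**5. What Statistical methods already fixes.** For all sleep and mental health outcomes: a linear mixed model with time, group and their interaction, random intercepts, a likelihood ratio test of the interaction, and time in weeks. Data collection methods defines sleep efficiency and duration.

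**6. What remains open.**

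- *Caseness* is yes/no, but only linear mixed models are named.
- *Diaries*: the Sleep diaries paragraph requests seven days and requires at least four to proceed at baseline. No rule says how nights become one value, or how many are needed at week 10.
- *Later visits*: nothing says whether they are modelled jointly or separately, or as a slope or as categories. Visit order also varies. For a woman randomized at 28 weeks of gestation, the gestational week 36 visit falls at study week 36 − 28 = 8, before the week 10 visit. Her week 18 visit would fall at 28 + 18 = 46 weeks, after delivery if delivery is at about 40.

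**7. Would coded arms be enough alone?** Sample size cites an effect of d = 0.95 on sleep efficiency against usual care in earlier work. If the primary result shows one coded arm clearly sleeping better, the analyst may guess which arm it is. Coding therefore protects later choices only if they are already settled when the primary comparison is run.

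**The case against.** The strongest reply is that these are gaps in prespecification, closed by writing the rules down, and that they would be just as open to a blinded analyst. Much of this stands. It would be too strong to say that the secondary analyses are unspecified, because the model, test and time scale are set. It is also why the remedy needs a script lock and not only coded arms. What does not follow is that the scope of blinding is irrelevant: until the rules are written, it matters whether the person writing them knows the arms.

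Several stronger readings are tempting, and the documents do not support them:

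- *The statistician will be unblinded for secondary analyses.* The plan is silent. Unblinding is permitted, not planned.
- *Exactly one comparison is covered.* The Blinding sentence uses the plural, and Objectives labels depressive symptoms primary for Aim 2. The count stays at 26 or 25 until Objectives and Outcomes agree.
- *Unblinding would come well before follow-up ends.* With delivery at 40 weeks, six months taken as 26 weeks, and entry at 28 or 8 weeks (8 is assumed), six months after birth falls (40 − 28) + 26 − 10 = 28 or (40 − 8) + 26 − 10 = 48 weeks after the week 10 visit. That is one participant's interval. A trial-level week 10 analysis would wait for the last participant. Protocol Amendments shows recruitment under way by 10 March 2017 and still open on 27 March 2018, a span of at least 54 weeks. A woman randomized in March 2017 would finish 38 to 58 weeks later. The last participant's week 10 visit comes no earlier than about 54 + 10 = 64 weeks. How much follow-up would remain cannot be derived.
- *There is no other safeguard.* Staff are blinded to outcomes during the trial. That protects conduct, not the choice of analysis.
- *Wider blinding is free.* It is not; the costs are given with the fix.

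**Conclusion.** The point holds as a minor, inexpensive improvement. The stated analyst blinding leaves out 26 of 27 Aim 1 and 2 comparisons, or 25 if EPDS at week 10 is primary. At least three substantive choices for those comparisons are not yet written down, and nothing prevents their being made with the arms known.

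The count assumes that diaries are collected only at week 10, and that each outcome at each visit is one comparison. It measures how far the commitment reaches, not how much bias would result; no size of bias can be calculated from the documents. A reader might infer that wider blinding would make the self-reported results secure. It would not: reporting bias from participants who know their arm is a separate problem, and analyst blinding leaves it untouched.

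**What to change.** Replace the sentence in Blinding with wording such as: *The study statistician will work with arms coded A and B for all primary and secondary analyses of Aims 1 and 2 at every time point. Scripts for all of these analyses, including follow-up, will be locked before the primary comparison is run and before the code is broken.*

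Three things go with it:

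- In the locked scripts, settle the model for caseness, the rule for turning diary nights into an outcome (with a minimum number of nights), and how later visits enter the model, including women whose visits fall out of order.
- Reconcile Objectives and Outcomes on whether EPDS is primary.
- Say who holds the code. The independent investigator who generates the allocation sequence could plausibly supply it, though the plan does not provide for this.

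The script lock is the essential part, because the labels may be guessed once the primary result is seen.

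The cost is small but not zero. Arms stay coded for longer, follow-up scripts are finished earlier than they otherwise might be, and session-adherence data, which reveal the arm, are withheld from the statistician until unblinding. Design, sample size and data collection do not change.

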Interventions. Digital CBT-I. The digital CBT-I program, Sleepio (www.sleepio.com), is delivered in 6 weekly web-sessions via website or iOS app. Treatment content is based on CBT-I manuals and includes a behavioral component (sleep restriction, stimulus control, and relaxation), a cognitive component (paradoxical intention, cognitive restructuring, mindfulness, positive imagery, putting the day to rest) and an educational component (psycho-education, sleep hygiene). The program is interactive, and content is presented by an animated virtual therapist. Participants schedule their session times and are prompted via email/SMS if they do not complete the session as scheduled. Participants complete daily sleep diaries throughout the intervention, which is used by the program to provide personalized help. Participants receive an email/SMS reminder each morning to prompt them to fill in their sleep diary. Additionally, study staff will monitor participant use of the website, and will contact any participants who have not logged on to the program or who have fallen behind in weekly sessions in order to discuss any challenges and troubleshoot barriers. Participants complete a short questionnaire at the beginning of the intervention to set treatment goals. Throughout the course of therapy, participants have access to an online community board and an online library of information about sleep. Participants will receive access to Sleepio at no cost as part of their participation.

Treatment as usual (TAU). The control condition is intended to reflect standard care for pregnant women with insomnia symptoms. No limits are placed on receiving non-study treatment, including medication or psychotherapy. Participants randomized to TAU will receive a free voucher code to Sleepio upon study completion.

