Participants will be sent reminders via their preferred method of communication after 3, 5, and 10 days of non-response. After 2 weeks of non-response, we will contact their secondary contact person. After 3 weeks of non-response, we will mail the primary outcome measure with a stamped and addressed return envelope. Every effort will be made to obtain outcome data from

participants who discontinue the intervention. If need be, participants who discontinue the intervention can opt to only complete the primary outcome measure to reduce time burden.

Data management. Qualtrics maintains data behind a firewall. All data is accessed only by the owner of the survey who must provide a user ID and a password. All pieces of data are keyed to that owner identification and cannot be accessed by anyone else.

REDcap is housed in a locked and guarded data center staffed at all hours. Entrance to the data center requires use of a card key to unlock the data center door and a second card key lock secures the cage that the servers reside within. The security of the data center is further protected by an Operations desk that is staffed 24x7 and by a security camera system. REDcap servers are guarded by multiple firewall and intrusion detection systems. All electronic connections to the REDcap environment are encrypted. The REDcap production system is comprised of a web server front-end and a MySQL database server back-end. The web server resides in a demilitarized zone to ensure that survey participants are able to access REDcap surveys from any device connected to the Internet. The MySQL server back-end resides in the protected ISU subnet that is protected by UCSF maintained firewalls. The data stored in the REDcap MySQL database server can be accessed by the REDcap end users by logging in and opening the REDcap project(s) that they have been granted access to by the owners of the projects. Only ITS and ISU system administrators are authorized to access the back-end database server directly by logging into the virtual private network for the database server resides in.

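### The ISI-only option is tied to discontinuing the intervention, so in practice it exists only in the CBT-I arm, and EPDS missingness can depend on arm and on stopping treatment

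*Combined protocol and SAP*

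**What the plan says.** The retention paragraphs of Data collection methods give two routes to a reduced assessment.

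- **Opt-in.** After promising every effort to collect outcomes from women who stop, the protocol adds that, if need be, "participants who discontinue the intervention can opt to only complete the primary outcome measure to reduce time burden".
- **Mailing.** "After 3 weeks of non-response, we will mail the primary outcome measure with a stamped and addressed return envelope". This step is not limited by arm or by discontinuation.

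The measure in question is the ISI. Under Outcomes: "The primary outcome is change in insomnia symptom severity (Insomnia Severity Index) from baseline to 10-weeks post-randomization". On the control arm, Interventions says: "The control condition is intended to reflect standard care for pregnant women with insomnia symptoms". TAU women receive Sleepio access only once they have finished the study.

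The EPDS has two ranks. Aim 2 speaks of "mental health outcomes, including depressive symptoms (primary) and anxiety symptoms, compared to TAU participants", while Outcomes lists it among the secondary mental health outcomes.

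Statistical methods specifies a linear mixed model for each outcome with time, group, their interaction and a random intercept. It states no missing-data assumption and no sensitivity analysis.

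**The concern.** A woman who takes the opt-in gives an ISI but no EPDS, GAD-7, PSQI, Sleep Condition Indicator or diaries at that assessment. The sentence sets no limit by visit, so she could do this at every follow-up. A TAU woman who finds the battery equally burdensome has no matching opt-in; she reaches an ISI-only form only through three weeks of non-response.

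The rule can therefore make EPDS missingness depend on both arm and stopping treatment. If the women who stop have a different EPDS course from those who continue, the CBT-I arm's EPDS is seen mainly in women who stayed on the program and is compared with TAU women not selected in that way. At stake is the depression contrast, the main result of Aim 2. The women concerned are in contact and answering at least one questionnaire, so part of this loss may be avoidable.

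**Working it through.** **The plan's own figure.** Sample size inflates 128 evaluable women for attrition: 128/(1 - 0.38) = 206.5, or 128/(1 - 0.384) = 207.8 with the cited 38.4%. This agrees with 208, or 104 per arm.

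**Inputs.**
- From the documents: n = 104 per arm; attrition of 4-22% in web-based CBT-I; alpha .01, the only alpha stated.
- Assumed, because the documents give nothing: the share p of CBT-I women without an EPDS because they took the option (4-22%, borrowing the attrition range as a proxy); the amount d by which their EPDS change is worse than that of other CBT-I women (0.3-0.5 SD of change); complete TAU data; alpha .05 as an alternative to .01.

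**Bias with no true average effect.** If the whole CBT-I arm averages zero, the women still observed average p × d better than zero. So bias = p × d.

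**Standard error** (SD units) = sqrt[1/104 + 1/(104(1 - p))]. At p = 0.04 this is 0.140; at p = 0.22 it is 0.148.

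**Null rejection rate** = P(Z > z - bias/SE) + P(Z < -z - bias/SE), with z = 1.96 or 2.576.

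| p | women lost | d | bias (SD) | rejection at .05 | rejection at .01 |
|---|---|---|---|---|---|
| 0.04 | 4.2 | 0.3 | 0.012 | 5.1% | 1.0% |
| 0.04 | 4.2 | 0.5 | 0.020 | 5.2% | 1.1% |
| 0.10 | 10.4 | 0.3 | 0.030 | 5.5% | 1.2% |
| 0.10 | 10.4 | 0.5 | 0.050 | 6.4% | 1.5% |
| 0.20 | 20.8 | 0.3 | 0.060 | 6.9% | 1.7% |
| 0.20 | 20.8 | 0.5 | 0.100 | 10.4% | 3.0% |
| 0.22 | 22.9 | 0.3 | 0.066 | 7.3% | 1.8% |
| 0.22 | 22.9 | 0.5 | 0.110 | 11.5% | 3.4% |

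**Partial uptake.** Suppose 22% discontinue, only half of them take the option, the effect is 0.30 SD in women who continue and zero in those who stop. The all-randomised effect is 0.78 × 0.30 = 0.234. The observed effect is (0.78 × 0.30)/(1 - 0.11) = 0.263. The excess is 0.029 SD, against 0.066 SD if all of them take it.

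**Does the mixed model remove this?** With baseline and one follow-up, the model adjusts the CBT-I follow-up mean in proportion to the difference in baseline EPDS between women with and without follow-up. If those baselines are equal, the adjustment is zero and the bias stays at p × d. A small simulation of such a model (150 runs, within-woman correlation 0.5 assumed, d = 0.5) gave 0.10 SD at p = 0.20, as the formula predicts. To the extent that observed EPDS values do predict the poorer course, the model recovers part of it.

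**The case against.** The case on the other side has substance.

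- **The mailed form.** A reader might infer that ISI-only data arise only in CBT-I, and that a TAU woman gives everything or nothing. The documents do not support this, because the mailing reaches non-responders in both arms. Only the opt-in is asymmetric.
- **A voluntary fallback.** The option applies if need be, behind a commitment to every effort. A reader might infer that the plan strips the EPDS from all non-adherent women. It does not: it lets women who discontinue (a term the protocol leaves undefined) choose less.
- **The counterfactual.** A woman who would otherwise have given nothing loses no EPDS, and the trial gains an ISI. The rule costs an EPDS only from women who would have answered it. The documents do not give that split, so the effect of the sentence could be near zero.
- **Direction.** That women who stop do worse is an assumption. Some may stop because they have improved, which would reverse the bias.
- **Size.** It is tempting to put the 38% attrition figure in as uptake, which gives 0.19 SD and 22% rejection at d = 0.5. That figure comes from computer-based depression programs and is not an uptake rate for this option. Complete TAU data is also a simplification, since the plan inflates both arms for attrition.
- **Priority.** Protecting the single primary outcome when burden threatens all data is defensible.

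All of this limits the claim. It does not remove the one-arm opt-in or the lack of any analysis that addresses it. Statistical methods does refer to two intervention groups, but reading TAU as something a woman can discontinue is strained; if both arms were meant, the sentence needs rewording anyway.

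**Conclusion.** The point holds as a weakness in the secondary outcomes, chiefly the EPDS. The opt-in is in practice confined to CBT-I, it can make EPDS missingness depend on arm and discontinuation, and the planned analysis does not deal with this.

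Under the stated assumptions the consequence runs from negligible (0.012 SD and 5.1% rejection at 4% uptake) to moderate (0.11 SD and 11.5% at 22% uptake with a 0.5 SD difference; 3.4% at alpha .01). It requires that women who stop do worse than their observed EPDS values predict, and that they would have completed the EPDS without the option. Bias toward CBT-I is possible, not shown. A reader might infer that the primary result is compromised; it is not, since the rule helps to retain the ISI.

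**What to change.** Replace the opt-in sentence with: *Any participant, in either arm, who after the usual reminders declines the full battery is offered a short set: the ISI first, then the EPDS; she may stop after the ISI.*

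Record, by arm and visit, who used the short set and why. Add a sensitivity analysis of the EPDS contrast that uses the retained ISI and discontinuation status, for example multiple imputation within arm. Imputation by discontinuation status needs some discontinuers with an observed EPDS, which is a further reason to ask for it. If follow-up has already closed, the recording (as far as the data allow) and the sensitivity analysis are what remains possible.

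Adding the EPDS to the mailed form is optional. It depends on the study's own arrangements for reviewing returned EPDS forms, and it lengthens that form from 7 to 17 items, which could affect returns.

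The cost is one sentence, ten more items for women who have stopped, and possibly somewhat more use of the short set in TAU. The GAD-7, PSQI, Sleep Condition Indicator and diary outcomes stay exposed to the same missingness, and reports should say so.
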